This study has limited risks for participants. 75 to 95% of participants will only undergo a malaria rapid diagnostic test (URDT) requiring a finger prick and receive a negative result. 5 to 25% of participants are expected to be found URDT positive. The specificity of the test is high compared to uPCR (99%) as well as predictive positive value (88%), ensuring that >9/10 of these positive individuals will be infected with *P. falciparum* and will benefit from the ACT treatment ([3], Appendix D). The safety of DP and single low dose primaquine are well-described, including among asymptomatic individuals [2,4]. The risk associated with treatment will be limited. All screening participants in group 1 will also be sampled for 50 μ L capillary blood using the same finger prick as used for the URDT, which does not aggravate the risk. All procedures on participants will be conducted by trained medical personal.

Participants will benefit from this study by acquiring knowledge of their infection status as individuals and as a community. Infected individuals will be treated, which will decrease the potential negative consequences of a long-lasting infection [5,6] without increasing the risk of a subsequent clinical episode [7]. Households where positive participants will be identified will receive additional guidance on measures to protect against vectors and be reminded to consult the village MP within 24h in case of fever onset. At the community level, treatment of asymptomatic carriers is expected in reducing significantly the number of infective individuals, thus limiting the infection of mosquitoes and decreasing the overall village transmission and malaria burden.

Interest of the research

The METF target area in Eastern Kayin State, Myanmar, is piloting strategies with potential applications for >20 countries in the 2020 horizon, and many more countries by 2030 since elimination is one of the Sustainable Development Goals. It is also a region of significant artemisinin resistance, and under the threat of the expansion of a multidrug resistant falciparum lineage spreading in the GMS. Strategies developed and tested in a context of antimalarial resistance are therefore extremely valuable for this region.

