7.5. Baseline Assessments

The baseline assessment (D0) will occur immediately after inclusion. Participants will be asked baseline demographic data (age, sex, visitor status, occupation and activities during the previous month) and baseline clinical data (temperature and history of fever over the previous week), which will be recorded in a logbook where each patient will be identified by a unique number printed on a sticker that will also be used to label the URDT, the sample(s) collected from the participant.

In **group 1 only**, participants will undergo a finger-prick from which capillary blood will be collected using the lancet provided by the URDT manufacturer in order to realize the URDT. From the same finger-prick, 50 μ L of capillary blood will also be collected on an EDTA microtube, labelled with a participant sticker.

The URDT will be read by a trained field worker following the manufacturer's instructions. If the test is positive, a second finger prick will be conducted in order to collect an additional blood sample on filter paper (3x 1cm blood spots), labelled with a participant sticker.

If the test is positive, a physical and clinical examination will be conducted. Female participants of child-bearing age will be asked if they are or could be pregnant and proposed to take a pregnancy test if unsure. History of malaria diagnosis and treatment during the previous week will be collected. The weight of the participant will be measured and history of previous allergies to drugs and specifically antimalarials will be collected. A curative treatment for *P. falciparum* malaria will be administered to falciparum-positive participant following a weight-adjusted dosage and according to each participant characteristics (see 8. intervention).

The willingness and ability of eligible participants to take a complete treatment will be assessed by the fieldworker, and the importance of completing the treatment will be discussed with the participant if

necessary. The first dose of treatment will be administered directly, and recorded in the logbook. An appointment will be set for the next dose on the following day.

Participants who declare being unable to attend supervised treatment for the next takes will be given the remaining doses (expected <2.5% of treatments initiated).

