7.8. Discontinuation/Withdrawal of Participants from Study

The follow-up and study outcomes are defined at the village-level and apply to village populations rather than individuals. An eligible village will be excluded from the study if:

- the MSAT intervention can't be conducted (refused by the community, impossible to access)
- the population size changes by $\geq 50\%$ between MSAT and follow-up survey.

Each participant has the right to withdraw from the study at any time.

In this study, systematic individual follow-up will occur during the MSAT intervention period and after the MSAT intervention to monitor demographics and clinical case incidence.

During the MSAT intervention individual follow-up will be conducted to ensure that a complete treatment is taken by all individuals found infected with *P. falciparum*. In the light of the threats of artemisinin-resistance, it will however be necessary to ensure that all falciparum-positive individuals are treated and that all individuals initiating a treatment take a complete curative course. Counselling will be provided to participants wishing to discontinue their participation. The counsellors will be members of the CE team with an extensive experience of interventions requiring the treatment of asymptomatic participants (filariasis and/or malaria mass drug administration campaigns in the region). In case the participant refuses to continue his/her antimalarial treatment course outside of the study, he/she will be offered to receive standard treatment for falciparum clinical malaria (AL+sld PMQ) from the village MP, or referred to the nearest health facility. The reason for withdrawal will be recorded in the MSAT logbook.

Individuals or households moving in or out of the village will be assessed during the M12 follow-up. Newcomers will contribute to the village follow-up and be included in the prevalence survey if they match inclusion criteria.

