8. INTERVENTIONS / INVESTIGATIONS

For all participants in the two groups, investigation will consist in 1 URDT (Malaria Ag P.f ultrasensitive, SD/Alere, Republic of Korea).

For *P. falciparum* URDT positive individuals in the two groups:

- collection of 3x1cm dried blood spots on filter paper
- administration of a supervised antimalarial treatment course to individuals for which a *P. falciparum* will have been detected by URDT.

Specifically in **group 1**, a population list will be collected in each village prior to MSAT campaign and all participants will undergo:

- collection of a 50µL-aliquot of capillary blood for each participant to the screening during the MSAT intervention.
- 1 URDT + collection of a 50µL-aliquot of capillary blood for each participant to the follow-up survey at M12.

A safe, recommended treatment of *P. falciparum* malaria will be administered to URDT positive individuals based on participant's characteristics:

- The standard regimen for participants without known antimalarial allergy, not pregnant and not breastfeeding, will be a 3-day supervised weight-adjusted DP course and a single low dose PMQ. The single low dose PMQ will be administered on the first day.
- Pregnant women and in their 2nd or 3rd trimester, and breastfeeding mothers, will receive a DP course but no PMQ.
- Pregnant women in their first trimester will receive an oral course of quinine+clindamycin (7 days).
- Individuals with known drug allergy to piperaquine will be treated with AL (+/- sld PMQ as per their pregnancy/breastfeeding status)
- Specific/complex cases will be assessed by a medic and referred to a health facility for treatment if necessary.

The treatment will be directly observed by the MSAT team.

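### The malaria-post treatment offered on withdrawal (section 7.8) does not take account of section 8's primaquine conditions or of primaquine already given on the first day

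*Combined protocol and SAP*

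**What the plan says.** Section 7.8 sets out what happens when someone wishes to stop treatment. Counselling comes first. The rule then begins "In case the participant refuses to continue his/her antimalarial treatment course outside of the study", and the participant "he/she will be offered to receive standard treatment for falciparum clinical malaria (AL+sld PMQ) from the village MP". The same sentence gives an alternative: "from the village MP, or referred to the nearest health facility". The section names no regimen for the facility, gives no criterion for choosing between the two routes, and requires only that the reason for withdrawal be logged.

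Section 8 sets the study regimens by participant characteristics:

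- **Standard regimen:** three days of dihydroartemisinin-piperaquine (DP) with one low dose of PMQ. "The single low dose PMQ will be administered on the first day".
- **Second or third trimester, or breastfeeding:** "breastfeeding mothers, will receive a DP course but no PMQ".
- **First trimester:** seven days of quinine and clindamycin, with no PMQ listed.
- **Piperaquine allergy:** AL, with or without "sld PMQ as per their pregnancy/breastfeeding status".

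Section 7.5 adds: "The first dose of treatment will be administered directly, and recorded in the logbook".

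**The concern.** Section 8 conditions AL plus PMQ on pregnancy and breastfeeding status. Section 7.8 names the same combination with no condition. It is also silent on PMQ the participant may have taken a day or two earlier. Field staff who follow 7.8 as written could therefore make an offer that does not fit the conditions the protocol sets for its own regimens.

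This is an operative instruction. Section 7.8 stresses, because of artemisinin resistance, that everyone who starts treatment should complete a curative course, so the rule is meant to be used. The risk statement in section 3 reads "The safety of DP and single low dose primaquine are well-described". It does not discuss a part course of DP followed by AL with a further PMQ dose.

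The protocol does consider recent treatment in the opposite direction. Section 6.3.2 excludes from screening people with a documented positive test who received AL and PMQ in the previous 7 days, although it does not give the reason for that period. Nothing comparable covers movement from the screening team to the MP.

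**Working it through.** The plan states no figure on this point, so the check is a comparison of the texts.

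**Step 1: has a course begun?** The trigger in 7.8 is a refusal to continue, so at least one dose has been taken. Section 7.5 has the first dose given directly at enrolment, and section 8 places PMQ on the first day of the standard regimen. A standard-regimen participant who stops after day 0 has therefore already had PMQ.

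**Step 2: compare the MP route with section 8.**

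| Participant who stops | Study regimen (section 8) | MP offer as written (7.8) | What is unreconciled |
|---|---|---|---|
| Standard regimen, after day 0 | DP; PMQ already taken | AL + PMQ | PMQ is offered a second time; 7.8 does not address this |
| Second/third trimester or breastfeeding | DP, no PMQ | AL + PMQ | PMQ is offered where section 8 omits it |
| First trimester | Quinine + clindamycin; no PMQ listed | AL + PMQ | The drugs differ, and PMQ is offered |
| Piperaquine allergy | AL; PMQ depends on status | AL + PMQ | The status condition is absent |

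The first row and the pregnancy and breastfeeding rows concern different people. Women treated without PMQ cannot receive a repeat dose of it.

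**Step 3: the facility route.** No regimen is named, so neither effect follows from it.

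**Step 4: does information travel with the participant?** Under 7.5 the first dose is recorded in the logbook and women of child-bearing age who test positive are asked about pregnancy. Breastfeeding and trimester are not listed there, but section 8 cannot be applied without them. No section says that any of this goes to the MP worker or the facility on withdrawal.

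**Step 5: scale.** The documents give no withdrawal rate. For group 1 the number treated can be bounded from 60 villages of 190 people (section 9.2.1) and 5–25% positive (section 3), assuming that everyone is screened:

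- 60 × 190 = 11,400 people
- 11,400 × 0.05 = 570 and 11,400 × 0.25 = 2,850 treated
- each 1% of those treated who stop after day 0: 5.7 to 28.5, or about 6 to 29 people

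These are denominators and a unit of scale, not an estimate of the number affected. That number also depends on who takes the MP route and what is given there. The figure of under 2.5% in section 7.5 cannot serve as a withdrawal rate, because it describes people given their remaining doses to take unsupervised.

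**The case against.** A reader might infer that 7.8 sends everyone who stops to the MP for AL and PMQ without exception, and so flatly contradicts section 8. The documents do not support that, for five reasons.

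- **There are two routes, and both are optional.** The treatment is offered after counselling, and facility referral stands in the same sentence. Section 8 likewise sends complex cases to a medic and, if necessary, to a facility.
- **The trigger is ambiguous.** The phrase about continuing outside the study could mean that the participant may first finish the same course elsewhere, with the MP offer made only if that too is refused. Either way a course has begun, so the reading affects how often the rule applies, not whether the gap exists.
- **Section 8 governs study treatment.** It does not address care after withdrawal. On repeat PMQ, 7.8 fails to deal with an earlier dose; it does not break a written prohibition.
- **The named combination may be a label.** The Appendix B footnote uses it for standard first-line treatment of clinical cases. Section 7.9 refers to general programme procedures for MP care, and these are not in the documents.
- **MP workers do more than give AL and PMQ.** Section 7.6.1 has them follow up quinine and clindamycin in first-trimester women according to their training.

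These points stand, and they limit the claim. They do not close the gap. No criterion assigns people to a route, 7.8 does not invoke the MP worker's training or programme procedures, and section 7.6.1 says nothing about later pregnancy, breastfeeding or PMQ already taken. Even as a label, the MP offer names PMQ without the condition that section 8 attaches.

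**Conclusion.** The point holds in a limited form. Followed literally, the MP route in 7.8 offers PMQ again to a standard-regimen participant who stops after day 0, and offers PMQ to a pregnant or breastfeeding woman who stops. The pregnancy and breastfeeding limb is a mismatch between two written rules. The repeat-dose limb is an omission in 7.8 that follows from section 8's timing.

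The conclusion rests on reading the MP offer as written and does not extend to the facility route. Whether MP workers would in practice give PMQ in these cases depends on procedures outside the documents. The number affected is unknown and may be small. No view is taken on which treatment rule is right.

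**What to change.** The sponsor's clinical team should reconcile sections 7.8 and 8. The revised 7.8 should state:

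- what the phrase about continuing outside the study means;
- who takes the MP route and who is referred to a facility;
- how PMQ already given is handled;
- how pregnancy and breastfeeding status bear on the offer.

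The clinical content of each is for that team to decide.

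Separately, the screening team should give the MP worker or facility the drugs and doses already taken and the pregnancy and breastfeeding status it needed in order to choose a regimen under section 8.

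The cost is one paragraph in 7.8 and one line on a referral slip. No extra visits, staff or study data are needed.

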7.9. Definition of End of Study

The end of the study will be 12 months after the MSAT campaign if the estimated prevalence measured by URDT in the field is $< 5\%$, with the upper limit of the confidence interval below 10%. If the estimated prevalence is $\geq 5\%$, a new round of MSAT will be triggered. The follow-up will be conducted until 12 months after the last MSAT or 36 months after the first MSAT.

The threshold of 5% URDT prevalence corresponds to a 7.5% prevalence by uPCR, which was found to be indicating the presence of a substantial reservoir previously.

The MP will remain to continue diagnosis and treatment of fever cases as per the general METF procedures.

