Following a successful pilot study initiated in 4 villages in 2013 [2], METF has conducted surveys to measure the prevalence of asymptomatic malaria infections. Villages with high prevalence of malaria (>40%) in which falciparum represented at least 20% of malaria infections, were defined as hotspots and treated with a 3-month mass drug administration campaign. These campaigns were very successful at depleting the reservoir of asymptomatic carriage of *P. falciparum* (Figure 2), which translated in a significant decrease in clinical episode incidence (Figure 3). In spite of its success, this strategy is difficult to scale up due to numerous constraints and was not considered by the Myanmar NMCP. However, the successful decrease in case incidence obtained by treating the reservoir of asymptomatic carriers sparks interest for a simpler and faster intervention, relying on mass screening and treatment (MSAT) rather than MDA (Table 1). Such approach was previously impossible due to the lack of sensitivity of standard RDT to detect asymptomatic infections. A newly available ultrasensitive RDT (URDT) shows a 50% sensitivity and 99% specificity compared to uPCR. This sensitivity is sufficiently high to allow accurate detection of high prevalence villages, and to warrant evaluation of the impact of a URDT-based screening and treatment intervention. MSAT is a method approved by the Myanmar NMCP and recommended by the WHO.

[figure not shown]

Figure 2: Impact of MDA on *P. falciparum* prevalence (95% confidence interval) comparing baseline and 12 months after MDA (n=40 villages) in villages equipped with MP and addressed with MDA between January 2015 and April 2016.

By design, an MSAT intervention using a field test will not identify all carriers. However, it is likely to decrease village level prevalence by 50%, and parasite biomass by >97%, since 87% of infections with parasite densities >1000 parasite/mL are expected to be identified. This depletion of the reservoir could be sufficient to durably modify the village-level transmission and initiate or accelerate the MP-driven decrease. Additionally, a URDT-based MSAT strategy could be an extremely useful tool to respond to malaria outbreaks. Indeed, by rapidly screening the population of a village where the incidence has reached alarm thresholds, parasite carriers could be rapidly identified and treated, leading to a rapid decrease in the reservoir and an interruption of the transmission.

[figure not shown]

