6.4.3. Follow-up MSAT

A follow-up MSAT will be triggered if the estimated URDT prevalence of the M12 survey is $\geq 5\%$. It will follow the same procedures as the baseline MSAT.

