7.6.3. Follow-up prevalence survey (group 1)

Twelve months after the beginning of the MSAT campaign in group 1 villages (high incidence), a population list will be collected again and a prevalence survey will be conducted in a sample of village inhabitants to perform URDT and collect a sample of 50µL for reference testing (sample size based on ability to measure a 90% decrease from baseline, see 9.2).

After the subsample of inhabitants has been surveyed, if the URDT prevalence is above 5%, the survey will shift to an MSAT round following the same protocol as baseline. If the URDT prevalence is below 5%, the positive individuals will be referred to MP for treatment and the survey will finish.

This survey will identify households from the MSAT campaign, but not match individual identification codes.

Since the procedures and interventions are similar to

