9.2.2. Sample size for prevalence comparison

9.2.2.1. Sample size for prevalence decrease evaluation at village-level

For each village, the sample size required for M12 survey will be calculated to measure a 90% prevalence decrease from baseline prevalence by reference method, with a 95%CI width of 200% of expected M12 prevalence if its value is expected <2% and of 100% of expected M12 prevalence if its value is expected>2%. This should result in a sample size of 60 to 120 samples per village, depending on village size.

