19. APPENDIX D: UNPUBLISHED DATA ON URDT PERFORMANCE

This data was presented as a poster at the ASTMH Conference in November 2017.

Table 1: Comparison of the detection methods to uPCR

		uPCR result: Pf DNA+		Properties (%)	
		Neg	PF		
Lab uRDT result	Neg	1469	91	Specificity (Sp)= 98.9	98.3-99.4
	PF	16	115	Sensitivity (Se)= 55.8	48.8-62.7
Lab RDT result	Neg	1483	143	Sp= 99.9	99.5-100.0
	PF	2	63	Se= 30.6	24.4-37.7
Microscopy result	Neg	1483	148	Sp= 99.9	99.5-100.0
	PF	2	58	Se= 28.2	22.1-34.8
Field RDT result	Neg	1477	163	Sp= 99.9	99.5-100.0
	PF	2	43	Se= 20.9	15.5-27.1
Field uRDT result	Neg	1413	122	Sp= 99.3	98.7-99.7
	PF	10	80	Se= 39.6	32.8-46.7
Quansys ELISA	Neg	1427	35	Sp= 96.1	94.98-97.0
	PF	58*	171	Se= 83.0	77.2-87.9

[figure not shown]
* Plasmodium DNA found in 26/58 (45%) in the 1st step of uPCR, but PF was not characterized by the 2nd step.

Table 2: Reference test results in 16 uRDT positive, uPCR PF negative samples

Interpretation of combined HRP2- and parasite-reference tests

- Probable falciparum (or mixed) infections (Plasmodium DNA + PfHRP2).
- Insufficient evidence of falciparum infection (PfHRP2 without Plasmodium DNA or non-falciparum DNA without PfHRP2).
- No evidence of malaria infection (no DNA and no HRP2).

uPCR	Quansys HRP2		
	Neg	PF	Total
Negative	3	3	6
P. vivax	2	1	3
Plasmodium spp.	1	6	7
Total	6	10	16

Figure 1: Parasite densities detected by each method**Table 3: Detection of asymptomatic PF infections according to parasite density.**

Number of infections detected by method (for lab uRDT and RDT: corresponding % of uPCR infections detected).

Detected by:	Parasitemia category (parasites/mL)						Total
	<10 ²	10 ² -10 ³	10 ³ -10 ⁴	10 ⁴ -10 ⁵	10 ⁵ -10 ⁶	>10 ⁶	
uPCR	41	67	52	32	13	1	206
Lab uRDT	5 (12%)	30 (45%)	38 (73%)	28 (88%)	13 (100%)	1 (100%)	115 (56%)
Lab RDT	2 (5%)	6 (9%)	22 (42%)	19 (59%)	13 (100%)	1 (100%)	63 (31%)

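### Section 7.9 equates the 5% field URDT cut with 7.5% by uPCR; Appendix D's field-read data put it at about 11%

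*Combined protocol and SAP*

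**What the plan says.** Section 7.9 ends follow-up of a village 12 months after MSAT if "the estimated prevalence measured by URDT in the field" is under 5%, "with the upper limit of the confidence interval below 10" percent. At 5% or more, a new MSAT round follows. The support offered for 5% is that "The threshold of 5% URDT prevalence corresponds to a 7.5% prevalence by uPCR", described as a level previously found to indicate a substantial reservoir. No derivation is given.

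The same trigger appears twice more. Section 6.4.3 reads "A follow-up MSAT will be triggered if the estimated URDT prevalence of the M12 survey is" at least 5%. Section 7.6.3 starts a round "if the URDT prevalence is above 5" percent; below 5%, positives are referred to the malaria post (MP) and the survey finishes.

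Section 7.5 has the URDT read by a trained field worker, and 7.7 says the month 12 survey follows the same procedures. Section 3 says the test "shows a 50% sensitivity and 99% specificity compared to uPCR". Appendix D, Table 1, reports lab-read URDT and a separate row headed "Field uRDT result", each against uPCR.

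**The concern.** The rule works on field-read results, but the stated uPCR equivalent looks like lab-read performance. Field sensitivity in Appendix D is 39.6%, against 55.8% in the lab. With lower sensitivity, a given URDT prevalence stands for a larger uPCR reservoir, so a 5% field cut should correspond to well over 7.5%.

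The stake is a treatment decision in each group 1 village. Villages between 7.5% and the true equivalent of the cut are ones the protocol itself regards as having a substantial reservoir, yet on average they would read below 5% and get no month 12 round. Infected residents who were not sampled, or whom the test missed, would then not be reached by the survey.

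**Working it through.** **Inputs** (Appendix D, Table 1, against uPCR)

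- Field URDT: Se = 80/202 = 39.6% (32.8 to 46.7); Sp = 1413/1423 = 99.3% (98.7 to 99.7).
- Lab URDT: Se = 115/206 = 55.8%; Sp = 1469/1485 = 98.9%.
- Section 3: Se 50%, Sp 99%.

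**Step 1. Try to reproduce 7.5%.** The misclassification correction is uPCR = (URDT − (1 − Sp)) / (Se − (1 − Sp)), with URDT = 5%.

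| Source | Calculation | uPCR equivalent of 5% URDT |
|---|---|---|
| Lab row | (0.05 − 0.0108)/(0.5583 − 0.0108) | 7.2% |
| Section 3, 50%/99% | (0.05 − 0.01)/(0.50 − 0.01) | 8.2% |
| Field row | (0.05 − 0.0070)/(0.3960 − 0.0070) | 11.0% |

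The stated 7.5% is not reproduced exactly by any row. The lab row is nearest; scaling 5% by its ratio of uPCR positives to URDT positives (206/131) gives 7.9%, so the two lab conversions bracket 7.5%.

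**Step 2. Can sampling error explain the gap?** The printed field limits most favourable to the plan (Se 46.7%, Sp 98.7%) give 0.037/0.454 = 8.1%. The least favourable (Se 32.8%, Sp 99.7%) give 0.047/0.325 = 14.5%. A bootstrap of the counts gives a 95% interval of 9.1 to 13.6%. Reaching 7.5% at Sp 99.3% needs Se = (0.05 − 0.925 × 0.007)/0.075 = 58%, above the field upper limit of 46.7%.

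**Step 3. Check without the formula.** In the field-read sample, URDT was positive in 80 + 10 = 90 of 1625 (5.5%) and uPCR in 202 of 1625 (12.4%). Scaling 5% by 202/90 gives 11.2%.

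**Step 4. Reverse direction.** At 7.5% uPCR, field URDT reads 0.075 × 0.396 + 0.925 × 0.0070 = 3.6%; lab URDT reads 5.2%.

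**Step 5. Effect on decisions.** Take a village of 190 residents (9.2.1) and every survey size from 60 to 120; 9.2.2.1 says "This should result in a sample size of 60 to 120 samples per village". Draw infected residents hypergeometrically (14, 19 or 29 of 190), then apply Se and 1 − Sp binomially. No round follows if the count is below 5% of n, rounded up. The table gives the chance of no survey-triggered round as a mean over sizes (range over sizes).

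| uPCR prevalence | Field performance | Lab performance |
|---|---|---|
| 7.4% | 79% (64–87) | 49% (39–62) |
| 10% | 59% (47–70) | 26% (15–41) |
| 15.3% | 26% (16–41) | – |

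With 50%/99%, the 7.4% row is 59% (46–69). The 15.3% row is the uPCR equivalent of the 16% reference-assay prevalence in 9.2.2.2, using the Quansys row (171/206, 1427/1485). Other village sizes, which are my assumptions, give a similar picture under field performance: 60 of 80 residents, 63% at 7.5% and 45% at 10%; 120 of 300, 75% at 7.3% and 52% at 10%.

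**Step 6. Meeting the 7.9 end definition.** Require a count below 5% and an exact 95% upper limit below 10%. The chance is 55% (27–79) at 7.4% uPCR and 36% (15–57) at 10%.

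**The case against.** The strongest reply is that 7.9 does not cite Appendix D and rests on prior field experience that the protocol does not show. That 7.5% came from lab-read data is an inference. Appendix D is one dataset, and it does not describe who read the field tests. Performance at month 12 may also differ: sensitivity depends on parasite density (Appendix D, Table 3), treating carriers may change the density mix, and HRP2 persistence could raise positivity. This stands as a reason to state a range, but not as support for 7.5%: no field evidence in the protocol gives that figure, and the printed limits stay above it.

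The consequences are also softer than the headline contrast suggests:

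- Against the rationale's 50%/99% the gap at 7.4% is about 20 points, not 30. Even under lab performance about half of such villages get no round, because only 60 to 120 people are sampled.
- Positives found below the cut are still referred for treatment, the MP stays open, and incidence-based routes to another MSAT remain (6.1.2.2, 7.1). Those routes respond to clinical cases, whereas the month 12 survey looks for asymptomatic carriage.
- The upper-limit clause already makes ending strict: at 42 of the 61 survey sizes the largest qualifying result is below 3.6%. It does not govern the MSAT trigger, which uses the point estimate.

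Finally, 5% may be an operational choice. It can be kept, but then it needs justifying as roughly 11% by uPCR.

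**Conclusion.** The concern holds. For field-read tests the stated equivalence is wrong on the protocol's own data: 5% URDT is about 11.0% by uPCR (8.1 to 14.5%), not 7.5%. Near 7.5% uPCR the cut would miss most villages in any one survey, roughly 20 to 30 points more often than under the 50%/99% or lab figures. The effect fades with prevalence: a little over half are missed at 10%, and most villages are re-treated at about 15%. A missed round is not the same as closure, since the upper-limit clause keeps some of these villages open.

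This rests on Appendix D field performance holding at month 12. The end-definition figures also assume an exact interval without finite-population correction, as the plan names no method. The primary incidence model and the baseline versus month 12 prevalence comparison are not affected. The correction should be made; confidence in the practical impact is medium.

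**What to change.** In 7.9, replace the 7.5% figure with about 11% by uPCR when the URDT is read in the field (8.1 to 14.5% across the Appendix D limits), noting the assumption that this performance holds at month 12. That is one sentence and needs no new data.

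Then choose one action level:

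- **If 7.5% by uPCR is intended**, use at least 3.6% field URDT for a new round and below 3.6% for MP referral, in 6.4.3, 7.6.3 and 7.9.
- **Otherwise keep 5%**, write it as at least 5% in all three places (7.6.3 currently leaves exactly 5% unassigned), and justify 11% by uPCR as the action level.

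Keep the upper-limit clause either way.

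Moving the cut is a trade-off for the sponsor. At 190 residents and sizes 60 to 120, under field performance:

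- **Gain:** no re-treatment falls from 79% to 54% (41–65) at 7.4% uPCR, and from 59% to 34% (22–47) at 10%.
- **Price:** rounds in villages at about 5% uPCR rise from about 9% to 28% (18–40), and at about 3% from 3% to 12%.
- **Side benefit:** survey sizes with a possible result that neither triggers MSAT nor meets the end definition fall from 53 to 11 of 61 (51 to 9 with a Wilson interval).
- **Limit:** at exactly 60 surveyed, both cuts trigger at 3 positives, so the lower cut needs at least 61 people to have any effect.
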